5.6.3 Additional secondary endpoints

All additional secondary endpoints will be presented using the mITT and PPS populations, and all individual data will be listed as well. No sensitivity analysis will be applied.

Measurement of Ataxia and Functioning

- SARA total score
- SCAFI total score
 - o 9HPT-D

Clinical Study Reference: IB1001-202

- 9HPT-ND
- o 8MWT
- PATA test

Descriptive statistics will be used to summarize the endpoints above at each visit.

The subscores of the SARA score (gait, stance, sitting, speech disturbance, finger chase, nosefinger test, fast alternating hand movements, heel-shin slide) will also be summarized for each visit using descriptive statistics. Stacked bar charts will be provided per visit, based on the subscores of the total SARA score.

Spaghetti plots of individual patient SARA total scores and the SCAFI total scores versus time will be made as well as a mean or median display versus time, depending upon the distribution, and corresponding two-sided 90% CI at each visit.

The average SCAFI subscores (8MW_avg, 9HPT-D_avg, 9HPT-ND_avg and PATA_avg) as determined according to Section 10.1, following the scoring manual, will also be summarized with descriptive statistics.

The changes in SARA total score, SCAFI total score, the SCAFI subscores (8MW_avg, 9HPT-D_avg, and PATA_avg) between Visit 2 and Visit 4, as well as the changes between Visit 4 and Visit 6 will be analysed using a one-sample t-test or a Wilcoxon Signed Rank test depending on the distribution of the data. The SCAFI subscore 9HPT-ND_avg will only be descriptively summarized in tabular format.

Measurement of Health-related Quality of Life

The results of EQ-5D-5L as well as the EQ-5D-Y will be combined into a 5-digit number presenting the health status of the subject. Frequency tables will be presented per visit for the 5 domains, as well as for the 5-digit number of the EQ-5D-5L and the EQ-5D-Y separately. In addition, EQ-5D-5L and EQ-5D-Y domain percentages will be presented in separate bar charts per visit, with all visits combined into one plot (if possible).

The EQ-VAS score will be summarized by visit using descriptive statistics for patients aged < and \geq 18 years combined. Spaghetti plots of individual patient EQ-VAS scores versus time will be made as well as a mean or median display versus time, depending upon the distribution, and corresponding two-sided 90% CI at each visit.

Measurement of Overall Neurological Status

The mDRS composite score and individual components (ambulation, language, manipulation, swallowing, seizures, and ocular movement) will be summarized using descriptive statistics at each visit. As graphical display, a stacked bar chart of the 6 mDRS subscores at each visit will be created. Spaghetti plots of individual patient mDRS composite scores versus time will be made as well as a mean or median display versus time, depending upon the distribution, and corresponding two-sided 90% CI at each visit.

Furthermore, changes in the mDRS composite score between Visit 2 and Visit 4 as well as between Visit 4 and Visit 6 will be descriptively presented in a summary table.

Measurement of Global Impression

Clinical Study Reference: IB1001-202

The three CGI-S scores (scored by treating physician, caregiver, and patient) will be summarized using descriptive statistics and frequency tables for each visit.

Bar charts will be presented for the three CGI-S scores, spaghetti plots of individual CGI-S scores versus time will be made as well as a mean or median display versus time, depending upon the distribution, and corresponding two-sided 90% CI at each visit.

Descriptive statistics and frequency tables will also be used to summarize the three CGI-C scores (treating physician, caregiver and patient) between Visit 2 and Visit 4, and between Visit 4 and Visit 6, and corresponding bar charts will be created.

The CGI-C scores for Visit 4 versus Visit 2, and for Visit 6 versus Visit 4 will be evaluated using descriptive statistics. Similarly, the CGI-C from Visit 2 to Visit 4 minus the CGI-C from Visit 4 to Visit 6 will be presented descriptively. In addition, the CGI-C measures for treating physician will be analyzed similar to the primary endpoint: the CGI-C from Visit 2 to Visit 4 minus the CGI-C from Visit 4 to Visit 6 will be compared to a difference of zero using a one-sample t-test or Wilcoxon signed-rank test.

Note that CGI-C is referred to as CGI-I in the eCRF.

It is important to realize that the CGI-S and CGI-C scores per visit for each patient as provided by the caregiver may be based on varying caregivers and hence additional variation is introduced. No correction for this variation can be done and a footnote will be added to the table to describe this situation.

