"Compared to the patient's condition (i) Visit 2 (prior to medication) versus (ii) Visit 4 (end of medication) OR (i) Visit 4 (end of medication) versus (ii) Visit 6 (end of washout) OR (i) Early Termination Visit versus (ii) previous visit, this patient is: 1=very much improved since the initiation of treatment; 2=much improved; 3=minimally improved; 4=no change from baseline (the initiation of treatment); 5=minimally worse; 6= much worse; 7=very much worse since the initiation of treatment."

The Clinical Global Impression of Change (CGI-C) – caregiver asks the caregiver one question:

"Compared to the patient's condition (i) Visit 2 (prior to medication) versus (ii) Visit 4 (end of medication) OR (i) Visit 4 (end of medication) versus (ii) Visit 6 (end of washout) OR (i) Early Termination Visit versus (ii) previous visit, how much has he/she changed: 1=very much improved since the initiation of treatment; 2=much improved; 3=minimally improved; 4=no change from baseline (the initiation of treatment); 5=minimally worse; 6=much worse; 7=very much worse since the initiation of treatment."

The Clinical Global Impression of Change (CGI-C) – patient asks the patient (*if able*) one question:

"Compared to how you were (i) Visit 2 (prior to medication) versus (ii) Visit 4 (end of medication) OR (i) Visit 4 (end of medication) versus (ii) Visit 6 (end of washout) OR (i) Early Termination Visit versus (ii) previous visit, how much have you changed: 1=very much improved since the initiation of treatment; 2=much improved; 3=minimally improved; 4=no change from baseline (the initiation of treatment); 5=minimally worse; 6=much worse; 7=very much worse since the initiation of treatment."

The CGI-C – clinician/caregiver/patient will be assessed at the time points designated on the schedule of events (Appendix 3A for "naïve" patients and Appendix 3B for "non-naïve" patients).

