6.1 Updated Efficacy Parameters

6.1.1 Measurement of Global Impression

The clinical global impression of severity and change will continue to be measured, with the questions for the physicians, caregivers, and patients modified to accommodate the Extension Phase visits.

Physician, Caregivers, and Patients (if able) will be asked to assess the CGI-S at each visit (Visit 7, Visit 8, Visit 9, Visit 10, Visit 11, Visit 12, and at the Extension Phase Early Termination visit, if applicable). The question is identical to that described in the Parent Study Section 6.1.5.

Physician, Caregivers, and Patients (if able) will be asked to assess the CGI-C at Visit 8, Visit 9, Visit 10, Visit 11, Visit 12, and the Extension Phase Early Termination Visit (if applicable).

The Clinical Global Impression of Change (CGI-C) - clinician asks the clinician one question:

"Compared to the patient's condition at:

(i) Visit 7 (extension phase baseline) versus (ii) Visit 8 (interim extension phase treatment visit) OR versus Visit 9 (end of extension phase treatment);

OR

(i) Visit 9 (end of extension phase treatment) versus (ii) Visit 10 (end of extension phase washout);

OR

(*i*) Visit 10 (end of extension phase washout) versus (*ii*) Visit 11 (interim extension phase treatment visit) OR versus Visit 12 (end of extension phase treatment period II);

OR

(i) Early Termination Visit versus (ii) the previous visit,

this patient's condition is: 1=very much improved since the initiation of treatment; 2=much improved; 3=minimally improved; 4=no change from baseline (the initiation of treatment); 5=minimally worse; 6= much worse; 7=very much worse."

135

The Clinical Global Impression of Change (CGI-C) - caregiver asks the caregiver one question:

"Compared to the patient's condition at:

(*i*) Visit 7 (extension phase baseline) versus (*ii*) Visit 8 (interim extension phase treatment visit) OR versus Visit 9 (end of extension phase treatment);

OR

(i) Visit 9 (end of extension phase treatment) versus (ii) Visit 10 (end of extension phase washout);

OR

(*i*) Visit 10 (end of extension phase washout) versus (*ii*) Visit 11 (interim extension phase treatment visit) OR versus Visit 12 (end of extension phase treatment period II);

OR

(i) Early Termination Visit versus (ii) the previous visit,

how much has he/she changed: 1=very much improved; 2=much improved; 3=minimally improved; 4=no change; 5=minimally worse; 6=much worse; 7=very much worse."

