14.2.43	Descriptive statistics on the change in mDRS composite score between Visit 2 and Visit 4, as well as Visit 4 and Visit 6 (mITT and PPS population)
14.2.44	Descriptive statistics of the mDRS composite score and 6 components at each visit (mITT and PPS population)
14.2.45	Mean or median plot versus time of the mDRS composite score (mITT and PPS population)
14.2.46	Spaghetti plot of the mDRS composite score versus time (mITT and PPS population)
14.2.47	Descriptive statistics of the mDRS composite score and 6 components at each visit according to subgroups (mITT population)
14.2.48	Frequency table of the 3 CGI-S scores (treating physician, caregiver and patient) at each visit (mITT and PPS population)
14.2.49	Descriptive statistics of the 3 CGI-S scores (treating physician, caregiver and patient) at each visit (mITT and PPS population)
14.2.50	Bar charts of the 3 CGI-S scores (treating physician, caregiver and patient) at each visit (mITT and PPS population)
14.2.51	Mean or median plot versus time of the 3 CGI-S scores (treating physician, caregiver and patient) (mITT and PPS population)
14.2.52	Spaghetti plot of the 3 CGI-S scores (treating physician, caregiver and patient) versus time (mITT and PPS population)
14.2.53	Frequency table of the 3 CGI-S scores (treating physician, caregiver and patient) at each visit according to subgroups (mITT population)
14.2.54	Descriptive statistics of the 3 CGI-S scores (treating physician, caregiver and patient) at each visit according to subgroups (mITT population)
14.2.55	Frequency table of the 3 CGI-C scores (treating physician, caregiver and patient) between Visit 2 vs Visit 4, and between Visit 4 and Visit 6 (mITT and PPS population)
14.2.56	Descriptive statistics of the 3 CGI-C scores (treating physician, caregiver and patient) between Visit 2 vs Visit 4, between Visit 4 and Visit 6, and Visit 4 vs Visit 2 minus the CI-CS score Visit 6 vs Visit 4 (mITT and PPS population).
14.2.57	Result of t-test or Wilcoxon test on the change of CGI-C score for treating physician Visit 4 vs Visit 2 minus Visit 6 vs Visit 4 (mITT and PPS population)
14.2.58	Result of t-test or Wilcoxon test on the change of CGI-C score for treating physician between Visit 2 and Visit 4, as well as Visit 4 and Visit 6 (mITT and PPS population)
14.2.59	Bar charts of the 3 CGI-C scores (treating physician, caregiver and patient) between Visit 2 vs Visit 4, and between Visit 4 and Visit 6 (mITT and PPS population)

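### Does the physician CGI-C test need a stated benefit direction, a clearer Visit 6 reference and corrected table titles before it can be relied on?

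*SAP*

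**What the plan says.** **The test.** In SAP 5.6.3, under Global Impression, "the CGI-C measures for treating physician will be analyzed similar to the primary endpoint", with the two-period difference compared with zero by a one-sample t-test or Wilcoxon signed-rank test. Protocol 8.5.2 likewise ties the physician CGI-C to the CI-CS analysis. SAP 5.6.1 gives the output for that analysis: mean difference, two-sided 90% confidence interval and one-sided p-value (or Hodges-Lehmann estimate, interval and p-value).

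**The descriptive part.** "The CGI-C scores for Visit 4 versus Visit 2, and for Visit 6 versus Visit 4 will be evaluated using descriptive statistics". SAP 5.6.3 also plans a descriptive display of the first-period rating minus the second-period rating.

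**The codes.** Protocol 6.1.5 gives "1=very much improved since the initiation of treatment; 2=much improved; 3=minimally improved; 4=no change from baseline (the initiation of treatment"), continuing to 7 for the worst category. CI-CS runs from -3 (worst) to +3 (best) in SAP 5.2 and 5.6.1. SAP 4.1.3 describes the CGI-C range in words only.

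**The Visit 6 question.** The question in Protocol 6.1.5 compares "i) Visit 4 (end of medication) versus (ii) Visit 6 (end of washout"). In the Extension Phase (Protocol Appendix 6, 6.1.1) the caregiver version reads "how much has he/she changed: 1=very much improved; 2=much improved; 3=minimally improved; 4=no change", with no mention of treatment start.

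**The table list (SAP 11.3).** Table 14.2.56, a CGI-C table, ends "between Visit 4 and Visit 6, and Visit 4 vs Visit 2 minus the CI-CS score Visit 6 vs Visit 4". Table 14.2.58 is "Result of t-test or Wilcoxon test on the change of CGI-C score for treating physician between Visit 2 and Visit 4", and likewise for Visit 4 to Visit 6.

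**Status.** SAP 5.1 treats everything except the primary endpoint as exploratory, with p-values below 0.05 indicative only.

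**The concern.** Three things stand out on a first reading.

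- **Direction.** A one-sided test is borrowed from an endpoint where higher is better and applied to a scale where lower is better, with no direction or recode stated. A programmer who copied the primary code unchanged would report the p-value for harm. Physician CGI-C is the only global impression measure with a formal test.
- **Visit 6 reference.** Labels 1, 4 and 7 refer to the start of treatment. A physician who followed the labels and ignored the question would rate Visit 6 against Visit 2. A score of 4 could then mean either no change since Visit 4 or a full return to the pre-treatment state, which are opposite findings in a treatment-then-washout contrast.
- **Tables.** Read literally, Table 14.2.56 subtracts a CI-CS score from a CGI-C score, and Table 14.2.58 tests each period separately with no null value, although the text describes these scores only descriptively.

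At stake would be a misreported secondary result or a contrast that mixes two reference points.

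**Working it through.** The documents give no sample size or power for CGI-C. The nearest figure is the primary endpoint's 76% power (SAP 2.4.1: mean 0.45, SD 1.02, 30 patients, one-sided 5%). It reproduces: noncentrality 0.45 / 1.02 × √30 = 2.42, critical value 1.699 on 29 df, power 76.3%. It is used below only for scale.

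**1. Direction.** Let a be the rating for Visit 2 to Visit 4 and b the rating for Visit 4 to Visit 6, on codes 1 to 7.

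- Raw contrast: a - b.
- Recoded as 4 minus score: (4 - a) - (4 - b) = -(a - b).

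The 4s cancel, so the null is zero under either coding, and only the sign of the estimate and of t changes. For a patient rated 2 on treatment and 6 after washout, the raw contrast is 2 - 6 = -4 and the recoded one (4 - 2) - (4 - 6) = +4. The matching CI-CS pair gives 2 - (-2) = +4. Since 1 is best and 7 worst, benefit on raw codes must be negative; nothing else is needed to fix the tail.

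Suppose the wrong tail were used. Borrowing the primary's effect size (an assumption), an observed difference of -0.45 with SD 1.02 and n = 30 gives:

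- standard error 1.02 / √30 = 0.186; t = -0.45 / 0.186 = -2.42
- lower-tail p = 0.011; upper-tail p = 0.989; they sum to 1
- 90% interval -0.45 ± 1.699 × 0.186, that is -0.77 to -0.13

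A p-value of 0.989 would sit beside an interval wholly on the benefit side and beside the planned frequency tables and bar charts. The slip would be visible, and the correct t-test p-value is one minus the reported one. Power in the wrong tail would be about 0.003%, but that describes a test the plan does not prescribe.

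**2. Visit 6 reference.**

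| Place | Reference for the Visit 6 rating |
|---|---|
| SAP 4.1.3 | Visit 4 |
| SAP 5.6.3 | Visit 4 |
| Protocol 7.1.6 (Visit 6 procedures) | Visit 4 |
| Protocol 6.1.5, question | Visit 4 |
| Protocol 6.1.5, labels 2, 3, 5, 6 | none named |
| Protocol 6.1.5, labels 1, 4, 7 | start of treatment |

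For the size of the ambiguity, let d be the points gained by Visit 4 and w the points lost by Visit 6, treated as additive (an assumption). Rated against Visit 4, the contrast is (4 - d) - (4 + w) = -(d + w). Rated against treatment start, it is (4 - d) - (4 - d + w) = -w. With d = 2:

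| Gain lost by Visit 6 | Against Visit 4 | Against treatment start |
|---|---|---|
| all (w = 2) | -4 | -2 |
| half (w = 1) | -3 | -1 |
| none (w = 0) | -2 | 0 |

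For a patient who improved, the label reading shrinks the contrast by d. How many physicians would rate that way, and what the eCRF item says (it is named CGI-I there), cannot be seen.

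**3. Tables.** The opening of Table 14.2.56 names the three CGI-C scores; its ending matches the CI-CS title of Table 14.2.3. Taken literally, a patient unchanged in both periods would score 4 - 0 = 4. SAP 5.6.3 and Table 14.2.57 both give the CGI-C contrast correctly. For Table 14.2.58, raw scores tested against 0 would be significant whatever happened: with mean 4 (no change), an assumed SD of 1 and n = 30, t = 4 × √30 = 21.9. The only meaningful null is 4 on raw codes, or 0 after recoding.

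**The case for a change.** The best argument for an edit is that a one-sided test should not leave its direction to inference, least of all when it points to an endpoint coded the other way. The SAP names the direction for CI-CS, CI-S and mDRS, and its conventions in section 10.1 have no CGI entry. The subgroup forest plots in SAP 5.6 may show a reference line at zero, whereas no change within one period is 4 on raw codes. The table list contradicts the text in other places too: Table 14.2.8 lists rank correlations although SAP 7 drops the intra-rater analysis, and Table 14.2.16 lists a test that SAP 5.6.2 rules out. An edit would cost a few lines.

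The textual facts all stand: there is no stated sign or recode, three labels are at odds with their question, and two CGI-C table titles do not match the text. What does not stand is the inference that a result depends on them. SARA and the timed tests are also lower-is-better with no sign named in the SAP, and Protocol 6.1.2 supplies it, just as Protocol 6.1.5 does here. The zero line on the forest plots is qualified as applying only where it makes sense. SAP 10.1 provides for unforeseen conventions to be documented separately, and SAP 11.1 refers to separate table templates. It is also not correct that the SAP leaves the Visit 6 reference open. If the form carries the Protocol 6.1.5 labels, rewording a document cannot alter ratings already given.

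**Conclusion.** No change to the plan follows. The missing sign is a gap that any analyst closes from the protocol codes; it leaves the null value and the size of the test statistic untouched. The Visit 6 reference is defined consistently as Visit 4 wherever the analysis is specified, so the label wording is a slip in the instrument description. At most it adds uncertainty to individual ratings, of 2 points in the worked example, and that figure assumes additive points and a physician who follows the label over the question. The table titles are copying leftovers, overridden by SAP 5.6.3 and Table 14.2.57.

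The effect on the primary endpoint is nil. No effect on the physician CGI-C p-value has been shown, and that p-value is only indicative for an exploratory endpoint. This conclusion rests on the test being read towards benefit, as its purpose implies, and on the estimate, interval and frequency tables being reported as planned. The eCRF wording is the one element that the documents do not let us check.

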5.6.4 Other additional statistical analyses

The following analysis will provide an estimate of intra-patient variability and provides information on the stability of the outcome evaluation. Note that, considering the high degree of variability within and between these patients, this is only a simple approach as results may be influenced by e.g. rater variability, disease progression or treatment effect.

The analysis will be done for the mITT population only, and only for the CI-S outcome of the videos. No sensitivity analysis will be applied, and no separate analysis will be performed for subgroups.

The Intraclass Correlation Coefficient (ICC) will be used as an index of reliability to measure agreement between pairs of observations for Visit 1 and 2, Visit 3 and 4, and Visit 5 and 6 respectively, presenting the proportion of the total variance in the observations that is due to the differences between pairs. The ICC takes on values between 0 (meaning no agreement) to 1 (perfect agreement), with and ICC >0.80 representing high reliability. No imputation for missing visits will be done, and the ICC can only be determined for subjects having data for both visits in the pairs. The ICC value and the corresponding 95% confidence interval will be presented in a tabular format, and for additional clarity the number of available pairs will be added as well.

5.7 Safety and tolerability evaluation

5.7.1 Adverse events

A treatment emergent adverse event (TEAE) is defined as an adverse event that appears during or after study treatment and was absent before.

Clinical Study Reference: IB1001-202

An AE overview table will be created displaying the number and percentage of subjects experiencing a treatment-emergent adverse event (TEAE) and the number of TEAEs for: any TEAE, any mild/moderate/severe TEAE, any related/unrelated TEAE, any serious AE, and any TEAE leading to study discontinuation.

Furthermore, all TEAEs will be tabulated by System Organ Class (SOC) and Preferred Terms (PTs) within each SOC according to the MedDRA terminology list, using frequency counts (number of subjects with at least one event, and number of events) and percentage of subjects with the event.

TEAEs will also be tabulated by severity (mild/moderate/severe) and by relationship to study medication (related/unrelated). Similar tables will be created for TEAEs leading to premature discontinuation, SAEs and deaths, if applicable. These summary tables will be presented by decreasing frequency of occurrence based on SOC and PT.

In addition, similar TEAE tables (overall, by severity and by relationship, premature discontinuation, SAEs, and deaths) by SOC and PT will be presented per treatment cycle, and frequencies and percentages will be determined for the active treatment cycle and the washout cycle. The treatment cycle is the period between start of first treatment at Visit 2 and 24 hours after last dose at Visit 4. The washout cycle starts 24 hours after last dose at Visit 4 until and including Visit 6.

The summary tables will be accompanied by individual subject listings of *all* AEs including information on AE number, actual AE description, date/time of start and end of AE (or ongoing), PT (MedDRA), SOC (MedDRA), severity, relationship, pre-dose (yes/no), seriousness, action taken, outcome and other information collected in the CRF for adverse events. Pre-dose AEs are not considered to be treatment-emergent, except in case of worsening during/after study treatment (to be collected as separate AE in the database). AEs starting prior to administration of the study drug will only be listed. In this listing, a clear distinction will be made between prior and treatment emergent events.

To address the study delays due to Covid-19 in reference to AE occurrences, AE incidence rates will also be determined per study cycle (treatment cycle and washout cycle). Incidence rate of adverse events is defined as the number of adverse event cases per patient-year(s). The calculation of the incidence rate is the number of cases (i.e. patient with an AE) divided by the sum of the follow-up time of all patient at risk (which will be all subjects receiving treatment). This calculation is accomplished as follows:

- Denominator: ∑p_i × t_i, where p_i = patient i and t_i= treatment duration of patient i in years (total # days divided by 365.25), where treatment duration is determined based on first and last (dose) date.
- Numerator: the total number of cases (note: a single patient can be counted more than once if the AE occurs on separate occasions)
- Incidence rate=numerator/denominator

The use of this measure implies the assumption that the incidence rate is constant over different periods of time. Since the calculation is done per cycle, the denominator (patient-years) is also determined per cycle, based on the patients available within that cycle.

Clinical Study Reference: IB1001-202

Separate listings will be created for SAEs and deaths, if applicable. The SAF population is used for the AE presentations.

